### **3.4.4. Handling of other missing data**

Missing values for scores other than the primary endpoint and those described in the previous section will be imputed using a LOCF approach, where applicable. In case of missing device data, where a LOCF approach would be meaningless, e.g., BG values or applied Insulin bolus and basal amounts, statistics will be calculated based on available information.

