## 2.10. Populations for Analysis

Due to the design of the study with a parallel phase between visits 1 and 4 and a one-armed phase in which all subjects will use the Accu-Chek® Solo micropump system, analysis will distinguish between these phases. Wherever appropriate, the treatment arm, to which a subject is randomized, will be denoted as “arm”, the current treatment as “trt” in listings and tables. E.g., a subject randomized to treatment arm B (MDI) will therefore have the analysis assignments B for both, arm and trt between visits 1 and 4, while the corresponding assignments will be B as arm and A as trt between visits 4 and 5.

The following populations are defined for analysis:

- The safety population (SP) is defined as all enrolled patients with data documented at at least one of the visits 1 to 5.
- The full analysis population (FAS) will follow the intention to treat principle, i.e., all subjects will be analyzed according to the treatment arm they are randomized to..
- The per-protocol (PP) population will be defined on a per visit basis. For a given visit, it will include all subjects that will have completed this visit and have no severe protocol deviations.

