## 4.2. Data for other Analyses

### 4.2.1. Questionnaires

#### 4.2.1.1. DTQ Questionnaire Change and Status Parts

As described section 4.1, the DTQ questionnaire consists of a change part in which subjects are asked for changes in their treatment satisfaction and of a status part, in which they are asked for their current rating. The change score (with V1 status score as covariate) will be used to analyze change compared to pre study status, while the differences between V4 and V5 (e.g., for subjects changing from MDI or the mylife™ OmniPod® therapy system to the Accu-Chek® Solo micropump system) will be calculated based on the respective “now” scores.

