#### 4.2.1.3. PAID-5 Questionnaire (Emotional Distress)

The PAID-5 questionnaire consists of 5 questions with answers ranging from 0 (Not a problem) to 4 (Serious problem). The total score will be calculated as the sum of the individual questions, resulting in a number between 0 and 20 where lower scores are better.

Missing individual answers will be treated in accordance to the procedure described for DTQ. If one answer is missing, the mean of the answers provided will be used to calculate the total

sum, otherwise the questionnaire will be treated as missing and the LOCF procedure will be applied.

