#### **4.2.1.4. Roche Questionnaire**

The Roche questionnaire consists of 28 questions covering six areas, namely “Diabetes manager” (5 questions), “Pump” (4 questions), “Changeover” (4 questions), “Adhesive pad” (3 questions), “Overall system” (7 questions), and “Miscellaneous” (5 questions). Answers in the first five of these areas range from 4 (Agree) to 0 (Disagree) where higher scores are better. The “Miscellaneous” area consists of 5 free text answers. Total area scores from the first five areas will be calculated as the sum of scores in this area while the total questionnaire score will be calculated as the sum of all scores of the questionnaire. The total score will therefore be between 0 and 92. The free-text answers in the “Miscellaneous” section will only be listed but not further analyzed.

Missing individual answers will be treated in accordance to the procedure described for the DTQ. If more than one answer is missing for an individual section, this section will be treated as missing. For completely missing questionnaires, the LOCF procedure described earlier will be applied. Otherwise, sum scores will be calculated as described for DTQ.

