#### 6.8. Secondary Endpoints Analyzed by Visit

The following secondary endpoints will be analyzed by study arm and visit. Additionally, since subjects in treatment arms B and C will be switched to Solo micropump treatment after Visit 4, within treatment arm analyses will also be performed where applicable, i.e. analysis will be performed on Visit 4 versus Visit 5 data within each of these two study arms and for completeness, also for arm A.

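### LOCF for questionnaire scores has no stop at the Visit 4 switch, so in arms B and C scores given on MDI or OmniPod can stand as Visit 5 values

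*SAP*

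**What the plan says.** - **General rule.** SAP 3.4.4: "Missing values for scores other than the primary endpoint and those described in the previous section will be imputed using a LOCF approach, where applicable". The only named exemption begins "In case of missing device data, where a LOCF approach would be meaningless" and covers items such as glucose readings and delivered insulin.
- **Questionnaire rules.** SAP 4.2.1.2 applies LOCF to DTQ part 2. For PAID-5 with more than one answer missing, SAP 4.2.1.3 says "otherwise the questionnaire will be treated as missing and the LOCF procedure will be applied". SAP 4.2.1.4 says "For completely missing questionnaires, the LOCF procedure described earlier will be applied". None names a visit at which carrying stops.
- **Early termination.** Protocol 6.3 asks subjects who withdraw after Visit 2 to attend Visit 5 as an early-termination visit. SAP 3.4.1 holds those data in the Visit 5 variables. If there are none, it takes the last visit available.
- **The switch.** Arms B and C move to Solo at Visit 4. For an arm B subject, SAP 2.10 says "the corresponding assignments will be B as arm and A as trt between visits 4 and 5". SAP 6.2.1 does the same for arm C, and summarises Visit 5 by arm and over all subjects.
- **The switch analysis.** SAP 6.8: "analysis will be performed on Visit 4 versus Visit 5 data within each of these two study arms". SAP 4.2.1.1 bases "the differences between V4 and V5 (e.g., for subjects changing from MDI" or OmniPod to Solo) on the status scores. Protocol 11.6 asks for the DTQ change from week 26 to week 39 in groups B and C.
- **Populations.** SAP 6.2 makes the FAS primary for all but safety analyses. The PP set is defined by visit in SAP 2.10: "For a given visit, it will include all subjects that will have completed this visit and have no severe protocol deviations".

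**The concern.** LOCF normally substitutes an old value for a current one on the same treatment. Here the last observation in arms B and C may belong to a different treatment. Visit 4 is scored on MDI or OmniPod and Visit 5 is meant to be scored on Solo. A value carried from one to the other carries no information about Solo, and it fixes the within-subject difference at zero.

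At stake is the estimate of what happens when subjects move to Solo, which Protocol 11.6 lists first among the secondary analyses, together with the by-arm and overall Visit 5 summaries. SAP 3.5.4 sets special Visit 4 rules for safety events and device use time, but has none for questionnaires.

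**Working it through.** **1. Which values can cross the switch (arms B and C, FAS)**

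| Situation | Visit 4 value | Visit 5 value under LOCF | Difference |
|---|---|---|---|
| Visit 4 done, Visit 5 score missing | observed on MDI/OmniPod | Visit 4 score carried | 0 |
| Left before Visit 4, no early-termination questionnaire | earlier score carried | same earlier score | 0 |
| Left before Visit 4, early-termination questionnaire done | DTQ change score: copied from that record (SAP 3.4.1). Status and PAID-5: source not stated | early-termination score, given on MDI/OmniPod | DTQ change score: 0. Others: 0 or a change on the old treatment |

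By questionnaire (Protocol 7.10), DTQ and PAID-5 are affected in both arms. The Roche questionnaire is affected in arm C only, because arm B first completes it at Visit 5. Arm C's form before the switch also omits questions 8 and 9.

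**2. The plan's own figure**

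SAP 2.8 gives means of 110 and 90, SD 30, two-sided alpha 0.05 and 90% power. The normal approximation is 2 × (1.96 + 1.2816)² × (30/20)² = 47.3, so 48. The t-test version is 48.3, so 49, with 90.4% power at 49. Then 49/(1 − 0.18) = 59.8, so 60. The stated 49 and 60 reproduce and this point does not touch them. The documents give no figure for the Visit 4 to Visit 5 contrast.

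**3. Effect on the mean switch change**

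Assumed: n = 60 per arm and k = 3, 6 or 11 values carried, so q = k/60 = 5%, 10% or 18.3%. If missingness is unrelated to change, the LOCF mean is (1 − q) × true mean, whatever the SD.

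| k of 60 | true change 20 | true change 10 |
|---|---|---|
| 3 | 19.0 | 9.5 |
| 6 | 18.0 | 9.0 |
| 11 | 16.3 | 8.2 |

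**4. Precision (further assumption: change 20, SD 30)**

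- Reported SE = √(E[s²]/60). For k = 11, E[s²] = (49 × 1300 − 60 × (49 × 900/3600 + 16.33²))/59 = 795.9, so SE = 3.64. For k = 3 and 6 it is 3.82 and 3.76.
- The LOCF mean's own sampling SD = √(60 − k) × 30/60 = 3.77, 3.67, 3.50.
- Observed-pairs SE = 30/√(60 − k) = 3.97, 4.08, 4.29.
- Estimate divided by SE is about 5.0, 4.8, 4.5 under LOCF, against 5.0, 4.9, 4.7 from observed pairs.

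Simulated coverage of the 95% t interval, with k of 60 normal changes set to 0:

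| Change, SD | k = 3 | k = 6 | k = 11 |
|---|---|---|---|
| 20, SD 20 | 94% | 89% | 71% |
| 20, SD 30 | 94% | 92% | 83% |
| 10, SD 30 | 95% | 94% | 92% |
| 5, SD 30 | 95% | 95% | 94% |
| 0, SD 30 | 95% | 95% | 95% |

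The loss of coverage is due to bias. It disappears as the true change approaches zero.

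**5. Direction when missingness is informative (subjects who started Solo)**

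Truth = (1 − q)·μ_obs + q·μ_miss. LOCF bias = −q·μ_miss. Observed-pairs bias = q·(μ_obs − μ_miss). With q = 0.10 and μ_obs = 20:

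| μ_miss | LOCF bias | observed-pairs bias |
|---|---|---|
| 20 | −2 | 0 |
| 10 | −1 | +1 |
| 0 | 0 | +2 |
| −10 | +1 | +3 |

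The two are equal in size at μ_miss = μ_obs/2.

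**6. Overall Visit 5 summary**

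With equal k in B and C, the share of values not given on Solo is 2k/180 = 6/180, 12/180 or 22/180 (3.3%, 6.7%, 12.2%).

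**The case against.** - **The qualifier in SAP 3.4.4 permits a stop.** A statistician could decline to carry scores across the switch without breaching the SAP, which already exempts data for which LOCF makes no sense. This stands: the plan allows the error but does not compel it. But an undefined qualifier is not a pre-specified rule, and the questionnaire sections repeat LOCF without limit.
- **The per-protocol set may cover it.** SAP 6.13.2 repeats the analysis of all variables in all populations. The per-visit PP set would drop subjects with no Visit 5, giving something close to observed pairs. This partly stands. The FAS remains primary, SAP 6.2 mentions PP only for the primary analysis, and it is not stated whether an early-termination visit counts as completing Visit 5.
- **Labelling.** A reader might infer that every such value is tabulated as a Solo score in the by-treatment tables. The documents do not support that. SAP 6.2.1 sets Trt by study phase and by the device assigned when the data were collected, so an early-termination record from before the switch would not clearly be labelled Solo. The label of an imputed value is not stated. What is clear is entry into the by-arm and overall Visit 5 summaries.
- **The inputs are borrowed.** The 20 and 30 are between-arm planning values for the change score. The switch contrast is within subject and rests mainly on status scores. SAP 2.8 makes no assumption about Solo against OmniPod, so a change of 20 has no basis in arm C. This stands for the coverage figures; the factor (1 − q) needs neither input.
- **Observed pairs is not always better.** This also stands (step 5), and is why the fix needs a sensitivity result. It does not apply to subjects who never started Solo, who have no switch to estimate.
- **The counts may be small.** The 18% is a whole-study maximum, subjects who leave after the switch are asked for a Visit 5, and SAP 6.13.1 does not list questionnaires among data expected missing at virtual visits. So 11 of 60 is an upper corner.

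**Conclusion.** The concern holds for the questionnaire switch analyses in arms B and C and for the Visit 5 summaries. As the SAP stands, scores given on MDI or OmniPod can be used as Visit 5 values in the FAS, including for subjects who never used Solo.

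If missingness is unrelated to change, the mean switch change is understated by the carried share: 5%, 10% or 18% for the assumed 3, 6 or 11 of 60. If the missing subjects would have worsened on Solo, the error favours Solo. Coverage depends on a change and SD that the documents do not give, and stays close to nominal for small changes.

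Two stronger inferences are not supported. The reported SE is below the observed-pairs SE, but it is not too small for the LOCF mean itself, and a false switch effect is not made more likely: coverage is 95% at zero change and the test statistic barely moves. Nor are the primary tests affected, since they compare arms at Visit 4 under SAP 3.4.1. The harm is confined to uncontrolled secondary comparisons, of which only the DTQ is tested. Priority is minor to moderate.

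**What to change.** Add to SAP 3.4.4 that, in arms B and C, questionnaire scores are not carried across Visit 4 in either direction for the Visit 4 versus Visit 5 analyses and the Visit 5 summaries. Leave SAP 3.4.1 unchanged for the primary endpoint. Then:

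1. Exclude from those analyses and summaries the subjects who never started Solo, identified from dispensing records, and any early-termination score given before the switch.
2. For subjects who started Solo but lack a Visit 5 score, use observed pairs or a repeated-measures model of observed values, and state the missing-data assumption. Show a sensitivity result with their change set to 0 and to a worsening.
3. Report the number excluded per arm.
4. State which Trt label an imputed value takes, and whether the per-protocol repeat in SAP 6.13.2 covers these analyses.

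The cost is one SAP paragraph, a flag for having started Solo, a date check on early-termination records, a restricted Visit 5 summary, a small sensitivity table and the exclusion counts. No new data are needed. The downside is a smaller analysed number in a secondary analysis.

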## **3.5. Coding Systems and Conventions**

### **3.5.1. Technical Aspects and Coding Conventions**

Tables, figures, and listings will be provided in the same PDF document. The PDF will have a DIN A4 format and include a corresponding table of content preceding the content of the file. Page orientation will be changed between portrait and landscape on a page-to-page basis depending on optimum placement.

### **3.5.2. Date Coding and Day Numbering**

The format for presentation of date variables will be DDMMYYYY. The format for presentation of time variables will be hh.mm.

Partially entered dates (e.g., only year or only year and month) will be completed, if they are necessary for the calculation of durations required for the statistical analysis. Deviations from this procedure will be reported and justified in the clinical investigation report.

All assessment dates will be related to the date of V2. The study day will be calculated as described below:

Study day = Date of visit – Date of V2 + 1.

### 3.5.3. Incomplete Dates

For a limited number of fields, the eCRF allows to enter incomplete dates in cases if the exact date is not known to the subject or the investigator, e.g., the date when diabetes was first diagnosed. For analysis, dates where only the year is known/given, July 1 will be used. If the month but not the day is known, 15 will be inserted as day. E.g., “2005” will be replaced by “01-Jul-2005” and “Sep-2010” will be replaced by “15-Sep-2010.

### 3.5.4. Special Handling of Visit 4

#### 3.5.4.1. Safety Events at Visit 4

Subjects randomized to treatment arm B (MDI) and C (OmniPod) will receive the Accu-Chek® Solo micropump system only at Visit 4. As a consequence, safety events (AEs and SAEs) cannot be assigned to either the randomized treatment or the Accu-Chek® Solo micropump system based on the date of the event alone. If an assignment to a device will be available from the investigator and confirmed by Safety, it will be used for the analysis. Otherwise, the event will be assigned to the Accu-Chek® Solo micropump system to guarantee conservative results.

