#### 3.5.4.2. Device Use Time

Subjects will receive their study device (Accu-Chek® Solo micropump system, MDI, or OmniPod®) at Visit 2. Additionally, as described above, study subjects randomized to arms B and C will utilize two devices at the day of Visit 4. Consequently, for all analyses utilizing the number of days a given device is used, use time will be calculated starting at Visit 2. For subjects randomized to treatment arms B (MDI) and C (OmniPod), the day of Visit 4 will be counted for

both, that is for the randomized device and for the Accu-Chek® Solo micropump system. For subjects in treatment group A, the Visit 4 day will however only be counted once.

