### 6.12. Evaluation of Safety Variables

The safety analysis will be based on the SP and on the device, a subject is using at the time, when a safety event occurs. Since all subjects in treatment arms B and C will receive an Accu-Chek® Solo micropump system at Visit 4 (week 26) and will use it until the end of the study, AEs and SAEs occurring at or after Visit 4 will be attributed to the Accu-Chek® Solo micropump

system. Distinction will be handled and documented according to the description in section 6.2.1.

All AEs will be coded using the Medical Dictionary for Regulatory Activities (MedDRA). Summaries of incidence rates of overall AEs and of individual AEs by MedDRA system Organ Class and Preferred Term will be prepared. Furthermore, summaries will be tabulated for all AEs, AEs by maximum severity, AEs by strongest causality to study device.

Summaries will include number of events, number of subjects affected, the percentages of all subjects for a given treatment, and the events per year of use for a given device.

Defective devices will be tabulated and listed by device type and treatment arm.

Deaths, SAEs and AEs leading to withdrawal will be listed separately.

Episodes (numbers) of the following AEs will be summarized:

- Symptomatic hypoglycemia
- Severe hypoglycemia (SAEs)
- Diabetic Ketoacidosis (SAEs)

The following ADEs are of particular interest:

- ADEs leading to replacement of device.

Incidence rates of all ADEs and of these ADEs and AEs of special interest (as captured on the AE Form in the eCRF) per 100 patient years will be calculated together with exact two-sided 95% CIs assuming that the number of special AEs observed in the study is Poisson distributed.

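### SAP 3.5.4.1 and 6.12 give different rules for adverse events on the day of Visit 4, so an event confirmed as belonging to MDI or OmniPod is counted for that device under one and for Solo under the other

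*SAP*

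**What the plan says.** **SAP 3.5.4.1 (Safety Events at Visit 4)** deals with arms B and C, who receive Solo only at that visit. It recognises that, for this reason, an event's date is not enough to tell which of the two devices it belongs to. It then gives a two-step rule. First: "If an assignment to a device will be available from the investigator and confirmed by Safety, it will be used for the analysis". Second, when there is no such assignment: "Otherwise, the event will be assigned to the Accu-Chek® Solo micropump system to guarantee conservative results".

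**SAP 6.12 (Evaluation of Safety Variables)** opens with a general principle: "The safety analysis will be based on the SP and on the device, a subject is using at the time, when a safety event occurs". It then turns this into a date rule for arms B and C: "AEs and SAEs occurring at or after Visit 4 will be attributed to the Accu-Chek® Solo micropump" system. For the mechanics it refers elsewhere: "Distinction will be handled and documented according to the description in section 6.2.1". It does not mention 3.5.4.1.

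**SAP 6.2.1 (Distinction of Study Phases)** sets the treatment variable by phase. Phase 1 runs from V1 to V4 and phase 2 from V4 to V5.

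**SAP 3.5.4.2 (Device Use Time)** accepts that "study subjects randomized to arms B and C will utilize two devices at the day of Visit 4", and counts that day as use time for both devices.

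**The concern.** Section 3.5.4.1 says the date cannot settle which device a Visit 4 event belongs to. Section 6.12 settles it by date. Both are written as the operative rule for the same tables, and a programmer working from 6.12 would not be led to 3.5.4.1.

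The outputs affected are those listed in 6.12: event counts, subjects affected, percentages, events per year of device use, and rates per 100 patient-years with exact Poisson intervals. Charging an event of unknown origin to Solo is a cautious default. Charging to Solo an event that the investigator has assigned to MDI or OmniPod, and that Safety has confirmed, is misattribution. It overstates Solo and understates the comparator.

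The denominators then no longer match the counts. Under 3.5.4.2 the comparator keeps the Visit 4 day in its use time, but under 6.12 it can never have an event on that day.

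**Working it through.** The SAP gives no figure to reproduce here. The check is a comparison of the rules, followed by a calculation of scale.

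**Step 1: the two rules applied to each possible arm B or C event on the day of Visit 4**

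| Device assignment | SAP 3.5.4.1 | SAP 6.12 | Agree? |
|---|---|---|---|
| Confirmed as MDI or OmniPod | MDI or OmniPod | Solo | No |
| Confirmed as Solo | Solo | Solo | Yes |
| None confirmed | Solo (default) | Solo | Yes |

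The conflict is confined to the first row. Arm A is unaffected because it uses Solo in both phases.

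**Step 2: does the cross-reference resolve it?** Section 6.12 sends the reader to 6.2.1. There V4 is both the end of phase 1 and the start of phase 2, so a Visit 4 event in arm B can carry treatment B or A, and one in arm C can carry C or A. The reference leaves the question open.

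**Step 3: exposure on the switch day.** Inputs: 60 subjects per arm (SAP 2.8), and 26 weeks on the randomised device followed by 13 weeks on Solo (SAP 2.4). Assumptions: no dropout and nominal visit timing.

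- Switch-day exposure: 2 arms × 60 × 1 day = 120 subject-days; 120 / 365 = 0.33 patient-years.
- Solo use in arms B and C: 120 × 13 / 52 = 30 patient-years. Share: 0.33 / 30 = 1.1%.
- All Solo use, adding arm A: 60 × 39 / 52 = 45, so 45 + 30 = 75 patient-years. Share: 0.33 / 75 = 0.44%.

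**Step 4: effect of one reassigned event on a rate.** Patient-years = subjects × weeks × 7 / 365.25. Shift per 100 patient-years = 100 / patient-years.

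| | Patient-years, no dropout | Shift | Patient-years, 18% of each arm contributing no time | Shift |
|---|---|---|---|---|
| MDI or OmniPod (each) | 60 × 26 × 7 / 365.25 = 29.9 | 3.3 | 24.5 | 4.1 |
| Solo (all arms) | (60 × 39 × 7 + 120 × 13 × 7) / 365.25 = 74.7 | 1.3 | 61.3 | 1.6 |

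The 18% is the maximum dropout rate allowed for in SAP 2.8. Treating every dropout as contributing no time is an extreme case, used only to bound the result.

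**Step 5: could such events arise?** Protocol 7.5 has AEs assessed and insertion sites examined at Visit 4, and Protocol 9.3.1.1 makes plaster reactions to the infusion set captured events. A finding recorded with that visit's date falls under both rules. The documents give no basis for estimating how many there will be.

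**The case against.** The strongest reply is that a specific rule overrides a general one. Section 3.5.4 is headed as special handling of Visit 4, was added deliberately in SAP version 1.1, and explains why it is needed. Section 6.12 starts from the same principle of device in use, and 6.2.1 refers to device assignment as well as study phase. On that reading 3.5.4.1 governs the switch day and 6.12 the rest of phase 2. This may well be what the sponsor intends, but neither section says so. Section 6.12 expressly covers events at the visit as well as after it, and it points to 6.2.1 instead. The document history lists the addition of 3.5.4 and no matching change to 6.12. That fits 6.12 not having been aligned, although minor editorial changes are not itemised.

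Several points about size do stand:

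- Only one of the three cases is in dispute, so few events can move.
- The direction under 6.12 is against Solo, so the sponsor's device cannot be made to look safer.
- Measured against all Solo use, the switch-day share is 0.44%. The figure of about 1% applies to arms B and C only.
- The 120 subject-days bound all switch-day exposure, not just the disputed events.
- SAP 6.12 specifies no between-device test of safety, and the DTQ hierarchy is not involved.

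These points limit the importance of the conflict. They do not remove it.

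**Conclusion.** The concern holds. For an arm B or C event on the day of Visit 4 with a confirmed assignment to MDI or OmniPod, the two sections give opposite answers, and the SAP does not say which governs. Followed literally, 6.12 discards a confirmed assignment that 3.5.4.1 requires to be used.

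The issue is minor. It concerns one day per subject in two arms and affects descriptive safety summaries only. For frequent events it will hardly show. For SAEs or other sparse events, one reassignment changes two devices' counts. It moves the comparator rate by about 3.3 to 4.1 per 100 patient-years and the Solo rate by about 1.3 to 1.6, over the range from no dropout to 18% of each arm contributing no time. Those figures assume 60 randomised per arm and nominal visit timing. The number of disputed events is unknown and could be zero.

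**What to change.** In SAP 6.12, change *at or after Visit 4* to *after the day of Visit 4*, and add: *events on the day of Visit 4 are assigned according to 3.5.4.1*. This keeps the sponsor's own more detailed rule and its default to Solo, and it allows the comparator to have events on a day already counted in its use time.

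Because 6.12 also relies on 6.2.1, a short note under the table there would close the remaining overlap. It should say that, for safety events in arms B and C on the day of Visit 4, the treatment variable follows 3.5.4.1.

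The cost is a sentence of SAP wording, plus the optional note. No new data are needed, since 3.5.4.1 uses a device assignment only where one is available.
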